PASS INFORMATION

Title	Association between use of desloratadine and risk of seizures, supraventricular tachycardia, and atrial fibrillation or flutter: A Nordic register-based study
Protocol Version identifier	205-00 version 1
Date of last version of protocol	23-Jun-2020
EU PAS Register No:	Study not registered
Active substance	Desloratadine, ATC code R06AX27; Pharmacotherapeutic group: Antihistamines – H1 antagonist
Medicinal products:	AERIUS, AZOMYR, and NEOCLARITYN
Product reference:	EU/1/00/160, AERIUS EU/1/00/157, AZOMYR EU/1/00/161, NEOCLARITYN
Procedure number:	Not applicable
Marketing authorisation holder(s) (MAH)	Merck Sharp & Dohme B.V. [name]
Joint PASS	No
Research question and objectives	To describe the use of desloratadine in the general population; to describe the incidence rates of first seizure, supraventricular tachycardia, and atrial fibrillation or flutter; and to examine the associations between desloratadine exposure and risk of first seizure, supraventricular tachycardia, and atrial fibrillation or flutter.
Country(-ies) of study	Denmark, Finland, Norway, Sweden
Author	[name] National Institute of Public Health University of Southern Denmark [name] Phone: ^{PPD} [REDACTED] E-mail: ^{PPD} [REDACTED]

Product: MK-4117

2

Protocol/Amendment No.: 205-00 version 1

VEAP ID NO: 9149

EPIDEMIOLOGY NO.(PE STUDIES ONLY): EP07044.004

Marketing authorisation holder(s) including MAH Contact Person	
PPD [REDACTED]
 
Center Merck Sharp & Dohme (Europe), Inc. [name]
 
PPD [REDACTED]

Merck Final Repository (RCAM) Date	25-Jun-2020
Date of Health Authority Approval of Protocol	Not applicable

Product: MK-4117

3

Protocol/Amendment No.: 205-00 version 1

VEAP ID NO: 9149

EPIDEMIOLOGY NO.(PE STUDIES ONLY): EP07044.004

SUMMARY OF CHANGES

Protocol Section	Change
N/A	N/A

TABLE OF CONTENTS

PASS INFORMATION	1
SUMMARY OF CHANGES	3
TABLE OF CONTENTS	4
LIST OF TABLES	6
LIST OF FIGURES	7
LIST OF ABBREVIATIONS.....	8
1 RESPONSIBLE PARTIES	9
2 ABSTRACT.....	10
3 AMENDMENTS AND UPDATES.....	12
4 MILESTONES	12
5 RATIONALE AND BACKGROUND	13
6 RESEARCH QUESTION AND OBJECTIVES	14
7 RESEARCH METHODS.....	15
7.1 Study Design.....	15
7.2 Setting.....	17
7.2.1 Inclusion criteria	18
7.2.2 Exclusion criteria	19
7.3 Variables	20
7.3.1 Exposure	20
7.3.2 Outcomes	22
7.3.3 Covariates	24
7.3.4 Other variables	28
7.4 Data Sources	28

DL	Desloratadine
DSUR	Development safety update report
EMA	European Medicines Agency
EU	European Union
ICD	International Classification of Diseases
IR	Incidence rate
IRR	Incidence rate ratio
MAH	Marketing authorization holder
MSD	Merck Sharp & Dohme, a subsidiary of Merck & Co., Inc.
NIPH	National Institute of Public Health, University of Southern Denmark
NSAE	Non-serious adverse event
PASS	Post-authorisation safety studies
PIC	Personal identification code
PPV	Positive predictive value
PRAC	Pharmacovigilance Risk Assessment Committee
PSUR	Periodic safety update report
PV	Pharmacovigilance
PY	Person-years
OTC	Over-the-counter
QBA	Quantitative Bias Analysis
SAE	Serious adverse event
SAP	Statistical analysis plan
SCRID	Self-controlled risk interval design
SD	Standard deviation
SVT	Supraventricular tachycardia

2 ABSTRACT

Title	Association between use of desloratadine and risk of seizures, supraventricular tachycardia, and atrial fibrillation or flutter: A Nordic register-based study
Protocol Number / Version	205-00 version 1
Date	29-May-2020
Author	[name], Professor, NIPH, University of Southern Denmark, Copenhagen, Denmark
Rationale & Background	
A post-authorization safety study was needed to assess the potential risk of desloratadine exposure on seizures, supraventricular tachycardia, and atrial fibrillation or flutter. PASS (P203) was submitted and the regulatory commitment was accepted as complete using data from Denmark, Finland, and Sweden in January 2020. The original commitment and its associated protocol (P203) included analyses on four countries, but due to delay in receipt of the data from Norway, the EMA allowed MSD to provide a final report without these data.
 
This protocol (P205) is a voluntary PASS including analyses as intended in the original study protocol (P203) of the Norway data both alone and in combination with the original three countries.

Research Question(s) & Objective(s)	To explore the use of desloratadine in the general population (Substudy 1); to describe the incidence rate of first seizure (Substudy 2A); to examine the associations between desloratadine exposure and risk of first seizure (Substudy 2B); to describe the incidence rate of supraventricular tachycardia (Substudy 3A); to examine the association between desloratadine exposure and supraventricular tachycardia (Substudy 3B); to describe the incidence rate of atrial fibrillation or flutter (Substudy 4A); and to examine the associations between desloratadine exposure and atrial fibrillation or flutter (Substudy 4B).

Study Design	Observational, nationwide, register-based study using person-specific linkage of data from the national population registers from Denmark, Finland, Norway, and Sweden (“Nordic countries”) including all individuals who redeemed a prescription of desloratadine and all individuals with a registered diagnosis of seizure, supraventricular tachycardia, or atrial fibrillation or flutter.
Population	The population consists of a cohort of desloratadine users, a cohort of individuals with seizures, a cohort of individuals with supraventricular tachycardia, and a cohort of individuals with atrial fibrillation or flutter. The general population of the four Nordic countries will be used to derive estimates of the risk time by age, year, and country.
Variables	
The exposure variable of interest is desloratadine for which current use (i.e., exposed period) will be defined as the period after each redeemed prescription equal to the number of days’ supply plus a 4 week grace period to account for intermittent use and a possible wash-out effect. To minimize exposure misclassification, we propose to use person time at least 26 weeks beyond the dispensing date of the last prescription as the “unexposed” reference period.
 
The outcome variables are first seizure, first supraventricular tachycardia diagnosis, and first atrial fibrillation or flutter diagnosis. Directed acyclic graphs (DAGs) were developed to identify the minimum sufficient adjustment set of confounders to include in the association analysis of each outcome.

Data Sources	Data will be obtained from nationwide population registers, including the national patient registers, the civil registration systems, and the prescription registers.
Study Size	The sample size is fixed, as it will consist of all individuals in four Nordic countries (Denmark, Finland, Norway, and Sweden) who have redeemed at least one prescription for desloratadine or who have received a diagnosis of seizure, supraventricular tachycardia, or atrial fibrillation or flutter.

Data Analysis	A descriptive analysis of desloratadine use in the general population will be performed. Furthermore, the incidence rates of seizure, supraventricular tachycardia, and atrial fibrillation or atrial flutter will be calculated. Among persons ever dispensed desloratadine, the associations between desloratadine exposure and first seizure, supraventricular tachycardia, and atrial fibrillation or flutter will be evaluated using Poisson regression of incidence rates accounting for confounding factors. Additional supplementary analyses will be performed.
Milestones	
Start of data collection:	31-July-2020
End of data collection:	15-August-2020
Final report of study results:	30-December-2020

3 AMENDMENTS AND UPDATES

None

4 MILESTONES

Milestone	Planned Date
Start of data collection	31-July-2020
End of data collection	15-August-2020
Registration in the EU PAS register	15-July-2020
Final report of study results	30-December-2020

5 RATIONALE AND BACKGROUND

Since market authorization, there have been a small number of adverse event reports of seizures and supraventricular arrhythmias in patients taking desloratadine (DL), but the case reports do not permit evaluation of the association. Denmark, Finland, Norway, and Sweden (hereafter also referred to as ‘Nordic countries’) offer unique opportunities for such a study by means of the existence of centralized registration of activities in the healthcare sector, covering complete populations over many years.

The European Medicines Agency (EMA) had previously requested that Merck Sharp and Dohme (MSD) consider options for a post-authorization safety study (PASS; Category 3 PV activity) to investigate whether there is an association between desloratadine (DL) use and seizures, supraventricular tachycardia, and atrial fibrillation or flutter in the general population. This PASS (P203) was submitted and the regulatory commitment was accepted as complete using data from Denmark, Finland, and Sweden in January 2020. Although the original commitment and its associated protocol (P203) included analyses on four countries, the data for Norway were very delayed and the EMA subsequently allowed MSD to provide a final report without these data.

This protocol (P205) is a voluntary PASS including analyses as intended in the original study protocol (P203) of the Norway data both alone and in combination with the original three countries. The findings for the analyses for all four countries (P205) will be submitted to the EU health authorities with the next PSUR. The only change from the original protocol’s (P203) study methods/design is the removal of the secondary analyses. The subsequent final report for this protocol (P205) will build upon the report with the three countries to be inclusive of all four as was the intent of the original PASS.

DL is a prescription oral antihistamine approved in the European Union (EU) for the relief of symptoms associated with allergic rhinitis and urticaria in both adults and children (Annex 5. Data from the Danish National Prescription Register (www.medstat.dk/en; accessed 28 May 2014) suggest that about 270,000 Danish citizens (about 5% of the population) purchase antihistamines with a prescription at least once annually. This figure has been rather stable since the year 2000. The number of Danish citizens who purchase DL by a prescription at least once annually has increased from 7,317 in 2001 to 51,564 in 2012. The number of Danish children aged 0–4 years who purchased DL with a prescription at least once annually has increased from 8 in 2001 to 6,815 in 2012. The number of Danish children aged 5–19 years who purchased DL with a prescription at least once annually has increased from 935 in 2001 to 11,447 in 2012. In 2012, children aged 0–4 years accounted for 37% of all children (0–19 years) who purchased DL at least once. The background incidence of unprovoked seizures is rare; approximately 0.4-0.6 per 1,000 population per year [Hauser, W. A. and Beghi, E. 2008]. Patients with epilepsy experience seizures; however, not all individuals with seizures have epilepsy and not all seizures evolve into epilepsy [Hauser, W. A. and Beghi, E.

2008]. A previous study described clinical observations of seizures induced by DL in four children [Cerminara, C., et al 2013].

Supraventricular arrhythmias include supraventricular tachycardia (SVT), atrial fibrillation (A-fib), and atrial flutter (A-flu). Through review of cardiac events reported since marketing authorization, the MAH determined that SVT and A-fib constituted a potential risk and that the reported cases were distributed across all age groups, not just children. In the present study, new onset SVT and a composite of new onset atrial fibrillation or flutter (A-fib/flu) will be examined as two separate outcomes. The incidence rate (IR) of SVT is reported to be 13/100,000 person-years for persons aged 19 years or younger, 27/100,000 person-years for persons aged 20–64 years, and 122/100,000 person-years for persons aged 65 years or older [Orejarena, L. A., et al 1998]. Wilke et al. (2013) [Wilke, T., et al 2013] reported the incidence of A-fib to increase markedly by age with 0.0016 cases/1,000 person-years in children (<15 years) and approximately 30 cases/1,000 person-years for persons aged 80 years or older. No data on the epidemiology of A-flu were available.

The present protocol proposes a study using registers from the four Nordic countries to describe the association between DL use and seizures, SVT, and A-fib/flu.

6 RESEARCH QUESTION AND OBJECTIVES

The research question is to examine the associations between DL use and seizures, SVT, and A-fib/flu in the general population.

Primary hypotheses (stated as null-hypotheses)

- There is no association between current DL use and first seizure.
- There is no association between current DL use and SVT.
- There is no association between current DL use and A-fib/flu.

Primary objectives

- Describe the use of DL during the study period in the general population overall and stratified by country, age, gender, calendar year, seasonality, severity of rhinitis, asthmatic status, and chronic urticaria status.
- Describe the IRs of the following outcomes in the general population:
 - Incident diagnosis of seizure;
 - Incident diagnosis of SVT; and

- Incident diagnosis of A-fib/flu.
- Compare the risk of incident seizure among persons while currently exposed to DL to the risk among the same persons while unexposed to DL for the total DL population and stratified by age, while adjusting for relevant confounding factors.
- Compare the risk of incident SVT among persons while currently exposed to DL to the risk among the same persons while unexposed to DL for the total DL population and stratified by age, while adjusting for relevant confounding factors.
- Compare the risk of incident A-fib/flu among persons while currently exposed to DL to the risk among the same persons while unexposed to DL for the total DL population and stratified by age, while adjusting for relevant confounding factors.

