7 RESEARCH METHODS

7.1 Study Design

The proposed study will be an observational (non-experimental), nationwide, register-based study using data from the Nordic national population registers. The associations between current DL use and seizures, current DL use and SVT, and current DL use and A-fib/flu will be assessed in analyses using person-specific linkage of data (Table 1). The cohort of all DL users will be used for describing DL use (Substudy 1). The cohorts of individuals who have had first seizure, SVT, or A-fib/flu will be used to examine the IRs of first seizure, SVT, and A-fib/flu in the general population (Substudies 2A, 3A, and 4A, respectively). A cohort study design among all DL users (i.e. a risk interval design including the DL-only cohort [Glanz, J. M., et al 2006]) will be used for the association between current DL exposure and first seizure, SVT, and A-fib/flu (Substudies 2B, 3B, and 4B, respectively).

Table 1 Overview of Substudies.

Primary objectives	
Substudy	Aim
1	Descriptive analysis of DL use in the general population
2A	Descriptive analysis of IR of first seizure in the general population
2B	Association between DL exposure and risk of first seizure
3A	Descriptive analysis of IR of first SVT in the general population
3B	Association between DL exposure and risk of first SVT
4A	Descriptive analysis of IR of first A-fib/flu in general population
4B	Association between DL exposure and risk of A-fib/flu

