Pharmacoepidemiological studies typically use dispensed days' supply as a surrogate for current drug exposure, assuming they are used every day. However, in contrast to medications for many chronic diseases, antihistamines may be used intermittently, as needed for symptoms. For the main analyses in the present study of the association between current DL use and outcomes of interest (Substudies 2B, 3B, and 4B), person time exposed to DL will be determined from dispensing records. "Current use" (i.e., "exposed" period) will be defined for each prescription as the sum of days' supply plus a 4 week grace period to account for intermittent use and a possible wash-out effect. If a new DL prescription redemption occurs during an exposed period (either during the period equal to the sum of the days' supply or the 4 week grace period), the exposure period extends from that date with a period equal to the sum of days' supply in the newly redeemed prescription plus a 4 week grace period. Note: Days' supply will be calculated from the quantity of tablets or amount of solution dispensed and the standard daily dose based on the age of the patient (i.e., 6-11 months: 1 mg/day; 12 months-5 years: 1.25 mg/day; 6-11 years: 2.5 mg/day; ≥ 12 years: 5 mg/day). Because the drug is used "as needed", it is quite possible that there may still be exposed days in the period after the latest exposed period (i.e., after the exposed period that includes the sum of the days' supply plus a 4 week grace period). To minimize exposure misclassification, we propose to use person time at least 26 weeks beyond the dispensing date of the prior prescription as the "unexposed" reference period. The "unexposed" period is actually a period with remote exposure to DL because dispensing of DL is a condition of entering the study population. We will refer to the "remote exposure" period as "unexposed" (For more details, see section 7.3.1 and [Figure 1](#)). The time between the exposed period and the unexposed period is considered neither exposed nor unexposed.

The advantage of using this design restricted to DL users, in which the same persons may have both exposed and unexposed periods, is that we reduce confounding due to time-independent factors associated with DL use.

The study is divided into six parts described below (For more details, see section 7.7).

1. Substudy 1

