Age	
For the descriptive analyses of DL use, age will be defined as the age of the purchaser at the date of prescription redemption and stratified into age groups (0–4 years, 5–19 years, 20–64 years, ≥65 years).
 
In the association studies, age is a time varying confounder; and therefore, risk time will be split up in years of age. We will evaluate whether age can be included as a continuous variable by examining the assumption of linearity. Alternatively, age will be included as a categorical variable.
	Civil registration system
Sex	Sex is a time-independent confounder and will be included as males versus females in both the descriptive and association analyses.	Civil registration system
Country	Country of residence is a time-independent confounder, as persons will be excluded if emigrating the country. Country of residence will be included with four categories, i.e. Denmark, Finland, Norway, or Sweden in both the descriptive and association analyses.	Civil registration system
Calendar year	
For the descriptive analyses of DL use, calendar year is defined as the year of prescription redemption.
 
In the association studies, calendar year is a time varying confounder; and therefore, risk time will be split up in calendar years.
	Prescription register
Seasonality	
For the descriptive analyses of DL use, seasonality is defined as the season (i.e., winter [December-February], spring [March – May], summer [June-August], and autumn [September-November]) when the DL prescriptions are redeemed.
 
In the association studies, seasonality is a time varying confounder; and therefore, risk time will be split up in seasons defined as winter (December–February), spring (March–May), summer (June–August), and autumn (September–November).
	Prescription register
Asthma status	Both for the descriptive and association analyses, asthmatic status is defined as a binary variable indicating whether or not a person has redeemed treatment for asthma defined as at least two prescriptions of inhalant steroids within a six-month period and/or contacts hospitals with a diagnosis of asthma (including both primary and secondary diagnoses) during a five-year period before first DL exposure. To distinguish persons treated for chronic obstructive pulmonary disease from those treated for asthma, first registered asthma treatment has to be redeemed when the purchaser was 45 years or younger.	National patient register and prescription register

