Confounders included in the minimum sufficient adjustment sets	Definition	Data source
Disease severity of rhinitis	Both for the descriptive and association analyses, severity of rhinitis will be defined as binary variable indicating whether or not a person has received treatment for severe rhinitis. Persons with severe rhinitis will be identified from the prescription register as persons who have redeemed immunotherapy at least once during a five-year period before first DL exposure.	Prescription register
Chronic urticaria	Both for the descriptive and association analyses, chronic urticaria status is defined as a binary variable indicating whether or not a person has a registered diagnosis of chronic urticaria in the five-year period before first DL exposure.	National patient register

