A cohort study among ever-DL users analyzing the association between exposed and unexposed time and first seizures will be performed for the total population and stratified by age. Current use (i.e., “exposed” period) will be defined for each prescription as days’ supply plus a 4 week grace period to account for intermittent use and a possible wash-out effect. Unexposed time will be defined as the period starting 26 weeks from the dispensing date of the prior DL prescription until the next DL prescription redemption, if any. A person who has redeemed at least one prescription of DL is included in the cohort and enters the cohort at the date of first prescription redemption. Study individuals are followed until occurrence of a seizure; occurrence of one of the conditions described in section 7.2.2; 31 December 2015; emigration; or death, whichever comes first. The association between exposure to DL and first seizure will be evaluated using Poisson regression of the IR of first seizure, and the measure of effect is the IRR. A person with prescription redemption of DL in Norway and Sweden within the first 6 months after establishment of the prescriptions registers will not be included in order to account for truncation bias. In addition we exclude persons with DL prescription redemptions within 6 months after immigrating to Denmark, Finland, Norway, or Sweden. The analyses will be adjusted for confounders identified from the DAG (i.e., country, age, sex, calendar year, seasonality, severity of rhinitis, asthmatic status, and chronic urticaria status) (Table 4). We will evaluate whether age can be included as a continuous variable by examining the assumption of linearity. Alternatively, age will be included as a categorical variable.

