- Identifying persons with asthma by use of register data is challenging due to the fact that the drugs used for treatment of asthma overlap with the treatment of chronic obstructive pulmonary disease (COPD). In order not to misclassify persons with COPD into the group of persons with asthma, we identify persons with asthma as those initiating asthma treatment before the age of 45 years. However, this means that for the part of the population aged 45 years or older, we will only have information on asthmatic status from the patient register in which hospitalized cases are registered. These cases are more likely to have severe asthma than those identified through the prescription register meaning that residual confounders may be more likely to occur among the population older than 45 years than those younger. A quantitative bias analysis examining the impact of misclassification of asthma on the results will be performed.

- Chronic urticaria is a very rare diagnosis given at highly specialized hospital units. This means that we expect a delay from onset of symptoms of chronic urticaria and the diagnosis of chronic urticaria of approximately 2-5 years. In the period between onset of disease and diagnosis, persons may receive antihistamines, including DL prescribed by the general practitioner, for their symptoms. Therefore, chronic urticaria may be underreported in the hospital register and the sensitivity of the measure is expected to be somewhat low. To get an impression of how important this misclassification will be in the present study, we will look at how many of the persons with a diagnosis of chronic urticaria have redeemed prescriptions of DL during the five years prior to the date of diagnosis. A quantitative bias analysis examining the impact of misclassification of chronic urticaria on the results will be performed.
- As in any association study, there is always the possibility of unmeasured confounders or residual confounding resulting from roughly categorized confounders that could affect the results of the study.

Variables used for inclusion and exclusion criteria

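### The objectives describe a same-person comparison, but the planned Poisson cohort model estimates a mixture of within- and between-person contrasts

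*Protocol*

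**What the plan says.** The three association objectives in Protocol section 6 share one form. For seizure it is to "Compare the risk of incident seizure among persons while currently exposed to DL to the risk among the same persons while unexposed to DL". This is to be done overall and within age groups, with adjustment for confounders.

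Section 7.1 names the design as "A cohort study design among all DL users". It gives as its advantage that "the same persons may have both exposed and unexposed periods", which is said to reduce confounding by time-independent factors.

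Section 7.7.2 fixes the model: "The association between exposure to DL and first seizure will be evaluated using Poisson regression of the IR of first seizure". The adjustment set is "country, age, sex, calendar year, seasonality, severity of rhinitis, asthmatic status, and chronic urticaria status", and sections 7.7.3 and 7.7.4 repeat it for SVT and A-fib/flu. In Table 4, "Sex is a time-independent confounder and will be included as males versus females"; country is also treated as time-independent.

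Under section 7.3.1, reference time starts 26 weeks after the last dispensing. A refill before that point opens a new exposed period, and no reference time accrues.

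Table 4 fixes asthma, severe rhinitis and chronic urticaria in the five years before first DL use. For urticaria the flag is "whether or not a person has a registered diagnosis of chronic urticaria in the five-year period before first DL exposure". Section 7.9 adds that "we expect a delay from onset of symptoms of chronic urticaria and the diagnosis of chronic urticaria of approximately 2-5 years", that DL may be prescribed in the meantime, and that the sensitivity of the rhinitis and urticaria measures is expected to be low. It promises a quantitative bias analysis for each of the three flags.

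**The concern.** A same-person comparison removes every confounder that is constant within a person, measured or not. A Poisson model without a person stratum does not. It also uses differences between people, and here those differences line up with exposure: someone who refills often supplies mostly exposed time, and someone with one dispensing supplies a short exposed window and long reference time. Annex 8 describes the effect of rhinitis severity on DL use as very strong. It also draws paths through shared causes, for example smoking to asthma (and so to DL) and smoking to seizure, and notes that smoking is not in the registers.

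The interpretation of the IRR is at stake. If frequent users have a higher baseline rate for reasons that the flags miss, the IRR can exceed 1 without any DL effect. A report that follows the wording of section 6 would then present a pooled cohort estimate as a same-person result in a safety submission.

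**Working it through.** **1. Is the model conditional on the person?** Sex and country do not vary within a person, and the three severity flags are fixed at first DL use. All five would cancel in a person-conditional model. Sections 7.7.2 to 7.7.4 enter them as adjustment terms and state no person stratum, conditioning or person effect, so the model as written is unconditional. None of the nine supplementary analyses in section 7.7.5 conditions on the person. Section 7.1 announces ten, and the SAP is not at hand, so one more may be specified there.

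**2. The plan's own yardstick.** Annex 7 solves (p1 − p2)² = (Zα + Zβ)² [p1q1/(En) + p2q2/((1−E)n)] for p1/p2. For seizure at ages 20–64: n = 215,000, E = 11.12/52, p2 = 1 − exp(−40 × 6/100,000), one-sided 5%, power 80%. The result is 1.30 (stated 1.3). The same calculation for SVT, with 27 per 100,000, gives 1.37 (stated 1.4).

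**3. Illustration with no DL effect.** All inputs are assumptions except 10/52, which is the exposed share for ages 0–4 in section 7.5.2. A share s of users is persistent, with 80% of time exposed, no reference time and R times the baseline rate. The others are exposed 10/52 of the time and supply all reference time, so the reference rate is 1.

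IRR = [0.8sR + (1−s)(10/52)] / [0.8s + (1−s)(10/52)]

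| s | R = 1.5 | R = 2 |
|---|---|---|
| 0.05 | 1.09 | 1.18 |
| 0.10 | 1.16 | 1.32 |
| 0.20 | 1.25 | 1.51 |

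For s = 0.10 and R = 2: (0.160 + 0.173)/(0.080 + 0.173) = 1.32. With the plan's 11.12/52 for ages 20–64, the s = 0.10 row becomes 1.15 and 1.29.

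**4. Let persistent users stop.** Suppose they refill for half of follow-up, so that about 40% of their time is exposed and 40% is reference. The others contribute half their time as reference, and s = 0.10.
- R = 1.5: exposed rate (0.060 + 0.173)/(0.040 + 0.173) = 1.094; reference rate (0.060 + 0.450)/(0.040 + 0.450) = 1.041; IRR = 1.05.
- R = 2: 1.188/1.082 = 1.10.

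**5. Simulation with no DL effect.** Assumed: 30% heavy users with 1.5 refills a year, 70% light users with 0.25 a year, 6 years of follow-up, 8 weeks exposed per fill, reference time from week 26. Heavy users hold about 61% of exposed time and 19% of reference time.

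| Rate ratio, heavy vs light | Pooled, crude | Pooled, flag with 30% sensitivity | Pooled, perfect flag |
|---|---|---|---|
| 1.25 | 1.09–1.10 | 1.06 | 1.00 |
| 1.5 | 1.20–1.21 | 1.15 | 1.02 |
| 2 | 1.35 | 1.26 | 1.00 |

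The crude figures follow from the time shares. At a rate ratio of 2, (0.609 × 2 + 0.391)/(0.187 × 2 + 0.813) = 1.609/1.187 = 1.36. A person-conditional model returned 0.98 to 1.02 throughout.

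A more extreme closed-form mix (60% with one fill, 30% with two fills a year, 10% with four, the last two groups at the raised rate) gives 1.32 and 1.60 for rate ratios of 1.5 and 2. The range from steps 3 and 4 is therefore not a bound.

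**The case against.** The strongest reply is that section 7.1 is open about the design. It calls it a cohort of all DL users, says only that the same people may have both kinds of period, and claims to reduce time-independent confounding, not to eliminate it. That is correct. A reader might infer from section 6 that a stated protection fails altogether, but the protocol does not claim full protection, and restriction to ever-users does help.

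A reader might also infer that the model simply compares heavy with light users. The documents do not support this. Everyone enters at a first redemption and contributes exposed time, and anyone who stops refilling accrues reference time after 26 weeks. Step 4 shows how far that shrinks the bias.

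A third inference is that flags fixed at first DL use cannot correct the problem. Step 5 contradicts it: a perfectly measured fixed flag removes the bias, so in that example low sensitivity is what leaves bias behind, not timing. The plan concedes the low sensitivity and commits to bias analyses. Supplementary analysis 3 also excludes person-time from a chronic urticaria diagnosis or a large redemption. These measures deal with the named flags. They do not yield a same-person estimate or address unmeasured fixed factors.

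Two further points limit the size of the concern. The seizure DAG has no arrow from rhinitis, asthma or urticaria to seizure, so a raised rate among frequent users would come through shared causes. And the protocol gives no value for R, the user mix or the flags' sensitivity.

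Finally, section 5 keeps the P203 methods apart from dropping the secondary analyses. That argues against altering the primary model, but not against clearer wording or one added sensitivity analysis.

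**Conclusion.** The mismatch stands. Section 6 words the objectives as within-person, while sections 7.1 and 7.7 fix an unconditional model that mixes within- and between-person contrasts. Time-fixed confounding is reduced but not removed.

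Under no DL effect and baseline rate ratios of 1.5 to 2, the illustrations put the unadjusted pooled IRR at roughly 1.05 to 1.5. The upper part of that range reaches the detectable IRRs of 1.3 and 1.4 at ages 20–64; the lower part does not. The figures rest on assumed mixes and rate ratios, leave out the planned adjustment except where a flag is shown, and depend strongly on how much reference time persistent users supply. They show what is possible and do not predict the bias in this study. A rate ratio below 1 would push the IRR the other way.

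It might seem to follow that the asthma, rhinitis and urticaria flags should be time-updated. That is not a necessary conclusion: updating at the record date mends neither the low sensitivity nor the 2–5 year diagnostic delay, and it departs from the P203 methods.

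**What to change.** 1. Reword the three objectives, and the conclusions of the report, as a comparison of exposed with unexposed person-time among DL ever-users, adjusted for the listed confounders. This costs only wording.

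2. Add one person-conditional sensitivity analysis per outcome (conditional Poisson, that is, self-controlled case series), with the same exposure classification and time splitting and with terms for age, calendar year and season. It uses cases only, so it is less precise, and it removes time-fixed confounding but not symptom flares around dispensing.

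   State its assumption that the event does not alter later DL use or observation. The cohort file stops at the event, so the cases' time has to be split onward to the remaining exit dates. For seizure, say how the section 7.2.2 censoring at the start of antiepileptic medicine is handled after the event, since a first seizure may itself trigger it.

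The cost is one extra model per outcome and some programming on data already obtained. The primary analysis, and its comparability with the three-country report, stay as they are.
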